### **1.3.** Rationale for the study

The Food and Drug Administration (FDA), has yet to release any proven reviews and standards on the components of e-cigarettes, nor the long- term effects of vaping (ALA, 2019). However, researchers have noticed the toxic chemicals and metals found in e-cigarettes. A few of the chemicals include nicotine, cancer causing carcinogens, and heavy metals such as nickel, tin, and lead. Also found in these products is benzene, which a chemical in crude oil and gasoline. There are many more dangerous chemicals in these products that most individuals are unaware of (ALA, 2019). The harsh chemicals found in vaping products, are directly linked to lung disease, difficulty breathing, spikes in blood pressure, rapid heart rate, gum disease, and many more.

This study will address the rise in vape products by providing education that will help prevent and decrease the percentage of students that currently vape.

### **1.4.** Hypothesis

We believe this program will make at least 50 percent of the participants more aware of the dangers and consequences of vaping, potentially lowering the rates of those participating in this habit while also preventing others from starting.

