Many vaping companies present their products as nicotine free and as being a safe and non-addictive way of smoking. From commercials to online ads, consumers are being told that this product is free from the smell of cigarettes, reusable, much cheaper, and even healthier than traditional cigarettes. This information can be very deceiving and persuasive to the young mind.

This program titled, “To Vape or Not to Vape”, will provide education to adolescents and young adults about the potential risk of vaping in an effort to assist with lowering the usage rates within the population. Content will include information about current statistics, potential short-term and long-term side-effects, and healthy alternatives for dealing with stress and peer-pressure. We anticipate that this program will increase this population’s knowledge about the risks of vaping products, and deter them from future use of the products. Effectiveness of this program will be measured by pre and post-tests.

**1.2.** Aim(s)/Objective(s)

The overall goal of this study is to increase knowledge of vaping and its associated risks. This study will find the patterns of vaping, and how it all started among adolescents. We want to know if students are aware of the serious and long term effects of vaping.

The objectives are:

1. To provide at least 100 middle school and high school students with anti-vaping education.
2. To provide at least 40 college students with anti-vaping education.
3. To improve the overall knowledge of vaping statistics and side effects as measured by a pre and post-test. The pre-test will be the baseline measurement. The post-test will be the measure of effectiveness. Out of the 10 questions on the post-test, the goal is to have the students answer at least 8 out of the 10 questions correctly.
4. To decrease the percentage of students who say that they are likely to vape in the future.

The program will be going to middle school, high school, and college campuses in the Dallas-Fort Worth (DFW) area to speak with students about vaping. The program will be implemented by community outreach, as the students will be presented with information about vaping and the resources necessary to prevent or stop vaping. This program will present the students with a 35-minute curriculum that is listed below. The purpose of this study is to relay

and publish data that will support education about vaping and the many health risks associated with vaping products.

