**2. OBJECTIVES AND STUDY OUTCOME MEASURES**

**2.1.** Study Objectives

**2.1.1.** Primary Objective(s)

The primary objective for this program is to obtain an understanding and gather information on the percentage of vape users in teens and young adults. This study will include at least 100 individuals, as this will allow us to determine why vaping is so prominent, what causes individuals to be attracted towards this habit, and determine why there is an increasing rate of vaping.

**2.1.2.** Secondary Objective(s)

The secondary objective for this program is to prevent those who do not vape to not begin to partake in this habit and to reduce the percentage pf the target population who are currently vaping, by increasing their knowledge on the dangers of vaping by 10%.

**2.2.** Study Outcome Measures

**2.2.1.** Primary Outcome(s)

We will obtain the percentage of vape users and their reasons for vaping from information gathered from pre-test (Appendix C). Within 6 months, we hope to see a decline in the usage of vapes in the DFW area.

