### 2.2.2. Secondary Outcome(s)

Changes in the degree of understanding will be assessed from the results of the pre- and post-test (Appendix C). In addition, we hope to find the answers to the following questions:

- Is vaping within the student's environment?
- Are the students being socially peer pressured into smoking, and if so how often?
- Are most students forming addictive behaviors towards vaping?
- What are the triggers that cause a student to vape?
- What is their reasoning on why they vape or participate in any smoking products?
- Do members of their close group of friends' vape?
- Are students aware of the serious and long-term side effects of vaping?

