## 5. STATISTICAL CONSIDERATIONS

## 5.1. Sample Size Considerations

A power analysis using the G-power 3.1 computer program (Faul & Erdfelder, 2009) indicated that a total sample of 35 people would be needed to detect a medium effect (Cohen's  $dz = 0.5$ ) with 80% power using matched-pairs Wilcoxon signed-rank test with alpha at 0.05 and assuming non-normal distribution. We need to enroll at least 44 subjects to account for 20% attrition rate. We plan to enroll 100 subjects in this study from whom we will collect pre- and post-test data on vaping.

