## 5.2. Statistical Analysis Plan

Descriptive analysis will be performed for all continuous variables. Mean  $\pm$  standard deviation will be presented for normally distributed variables and median  $\pm$  interquartile range will be presented for non-normal variables. Count and proportions will be presented for all categorical variables. All normally distributed continuous outcomes will be analyzed with paired t test and non-normally distributed continuous outcomes will be analyzed with nonparametric Wilcoxon signed-rank test. All Categorical outcomes will be analyzed using McNemar test.

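### Three different, unlinked knowledge targets are stated, the planned tests do not show whether any was reached, and the 8-of-10 mark requires every scorable item correct

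*Combined protocol and SAP*

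**What the plan says.** Three sections give a numerical target for knowledge.

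- Section 1.4 (Hypothesis) expects the program to make "at least 50 percent of the participants more aware of the dangers and consequences of vaping". This is a share of participants. What counts as more aware is not defined on any item or score.
- Section 2.1.2 (Secondary Objective) aims to prevent and reduce vaping "by increasing their knowledge on the dangers of vaping by 10" percent. This is a size of change. It does not say whether relative or in percentage points, or whether per student or for the group mean.
- Section 1.2, objective 3, says that "the goal is to have the students answer at least 8 out of the 10 questions correctly". This is an absolute post-test score. It uses no baseline and names no share of students who must reach it.

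The outcome in Section 2.2.2 is general: "Changes in the degree of understanding will be assessed from the results of the pre- and post-test". No score, key or threshold is given.

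Section 5.2 assigns tests by type of variable. "All normally distributed continuous outcomes will be analyzed with paired t test", while "non-normally distributed continuous outcomes will be analyzed with nonparametric Wilcoxon signed-rank test". For the rest, "All Categorical outcomes will be analyzed using McNemar test". It names no knowledge endpoint, responder definition or success rule. The power analysis in Section 5.1 "indicated that a total sample of 35 people would be needed to detect a medium effect" (dz = 0.5), which is tied to none of the three targets.

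**The concern.** A share of students who change, a size of change and an absolute final score are different quantities, and one set of results can meet one target and miss another. With no target named as the deciding one, and with tests that ask only whether there was any change, the reading of the knowledge result is open until the data are in. This matters because Section 1.2 makes greater knowledge the overall goal, takes the post-test as the measure of effectiveness, and intends the data for publication.

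The 8-of-10 mark has a further problem. It assumes ten questions that can be right or wrong, and the post-test in Appendix C does not contain ten.

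**Working it through.** **1. The plan's own sample size.** Inputs from Section 5.1: dz = 0.5, power 80%, alpha 0.05, Wilcoxon signed-rank. Taking alpha as two-sided (not stated) and the asymptotic relative efficiency 3/π for a normal parent: effective n = 35 × 3/π = 33.4, noncentrality = 0.5 × √33.4 = 2.89, power 80.1%. So 35 reproduces. Attrition: 35 / (1 − 0.20) = 43.75, rounded up to 44, as stated. These figures are not in dispute.

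**2. What significance would show.** With the planned 100 subjects all completing, the smallest significant observed dz in a two-sided paired t test is 1.984 / √100 = 0.198. That is a statement about zero change, not about any target.

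**3. Scorable items.** Post-test item 8 asks about feeling pressured to vape and item 10 about likelihood of vaping. Neither has a correct answer. The other eight (1-7 and 9) match pre-test items 5-11 and 13. No answer key is printed, so I assume that each of these has one intended answer. Then 8 of 10 correct means 8 of 8.

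**4. Constructed data, 100 students, score out of 8.** Relative gain = mean change / pre-test mean. Points = mean change / 8.

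| Before | Change | Share improved | Relative gain | Points | Share at 8 |
|---|---|---|---|---|---|
| all 6 | 55 gain one | 55% | 0.55/6 = 9.2% | 6.9 | 0% |
| all 4 | 40 gain three | 40% | 1.2/4 = 30% | 15.0 | 0% |
| 75 at 8, 25 at 7 | 20 gain one | 20% | 0.2/7.75 = 2.6% | 2.5 | 95% |
| all 4 | 60 gain one | 60% | 0.6/4 = 15% | 7.5 | 0% |
| all 6 | 20 gain one | 20% | 0.2/6 = 3.3% | 2.5 | 0% |
| all 5 | 85 gain three | 85% | 2.55/5 = 51% | 31.9 | 85% |

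More aware is read here as any gain in score. Row 1 meets the 50% target and misses 10% on either reading. Row 2 does the reverse. Row 4 meets or misses 10% according to how it is read. Row 5 meets none. Row 6 does well on all three. Both the paired t test and the signed-rank test give p < 0.0001 in every row.

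**5. Simulation.** Assumptions, none from the documents: 8 items, a normal person effect on the logit scale with SD 0 to 1.5, 200,000 students, and two extremes for item persistence (items re-answered afresh, or kept once right).

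| Mean percent correct | Relative gain | Points | Share improved | Share with all 8 right |
|---|---|---|---|---|
| 50 to 55 | 10% | 5 | 33-48% | not needed here |
| 50 to 60 | 20% | 10 | 55-57% | 2-15% |
| 50 to 80 | 60% | 30 | 83-94% | 17-38% |

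Hand checks at SD 0. For 50 to 55 with items kept once right, each wrong item is learned with probability 0.05/0.50 = 0.10, so an item is gained with probability 0.50 × 0.10 = 0.05, and 1 − 0.95^8 = 33.7% improve. For an average of 80%, 0.80^8 = 16.8% get all eight right.

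**The case against.** A reader might infer that the three targets are incompatible. They are not: the last row of the constructed table does well on all three. In the 50-to-60 and 50-to-80 simulated cases the 50% target and the 10% target are met together. The supportable statement is that the targets are non-equivalent and can disagree.

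A reader might also infer that a low share reaching 8 is a failure. Section 1.2 sets no required share, so that target gives no verdict as written. That is a gap in the target, not evidence of conflict.

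It is also too strong to say that Section 5.2 tests nothing relevant. It would test a knowledge change against zero, and McNemar could compare the proportion at the mark before and after. What is missing is a responder definition that brings McNemar into play and any test or interval read against a stated target.

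The strongest defence concerns stakes. Knowledge change is a secondary outcome in Section 2.2.2. The three figures are worded as a belief, an objective and a goal, with no decision attached, and they may concern partly different content (dangers in 1.4 and 2.1.2, statistics and side effects in 1.2). This stands in part: the documents do not show that anyone intends to pick a target afterwards. It leaves the risk in place, because no text says which figure decides. It does not touch the 8-of-10 error, which follows from the questionnaire.

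**Conclusion.** The point holds in this form: three different, unlinked knowledge targets, no stated way to judge any of them, and one mark that is wrong as written.

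The clearest disagreement is a mean rise from 50% to 55% correct. It meets a 10% relative target and misses a 10-point one, while about 33-48% of students improve, short of 50%. The mark asks for a perfect score on the eight scorable items, which 17-38% of students would reach at an average of 80% correct. These ranges depend on the assumed 50% baseline, the person SD of 0 to 1.5 logits, the two persistence extremes, and reading more aware as any gain in score. Two conclusions do not depend on the model: the targets can disagree, as the constructed data show, and significance does not establish any of them. That 8 of 10 means all eight scorable items follows from Appendix C, given one intended answer for each of those items.

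**What to change.** 1. In Section 5.2, define the knowledge score as percent correct on the eight scorable items common to both tests (pre-test 5-11 and 13; post-test 1-7 and 9), and attach the answer key.
2. In Section 1.2, restate the mark on those items. 80% of 8 is 6.4, so at least 7 of 8. State the share of students expected to reach it.
3. Name one knowledge criterion, in the same words, in Sections 1.4, 2.1.2 and 5.2. One option is the mean change in percent correct with a 95% CI, read against the 10% target, stating whether that is points or relative. Which criterion decides is the sponsor's choice; it has to be made before the data are seen.
4. Report the share improved and the share reaching the mark as descriptive results with CIs.

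Steps 1 to 4 are wording only and need no more subjects. The sponsor gives up the choice of target after the data are seen.

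There is one practical dependency. The paired analysis and the share improved need each student's two papers linked. The study is anonymous: Section 3 lists age, gender, race and zip code, and Section 6.3 zip code and grade level, which may not separate students in a class of 20 to 30. A shared anonymous number printed on both tests would link them. Section 6.2 requires IRB review of any amendment; Section 10 lists $345 ($448.50 with indirect cost) for one without a revised consent form.

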#### **1.4.1.** Primary Hypothesis

By increasing the awareness of vaping products, the number of vape users in teens and young adults will decrease by 5%. The students that participate in this program will obtain the knowledge of risk and side effects from smoking tobacco,

and the use vaping products. The program's goal will be measured by a pre and post survey.

**1.4.1.** Secondary Hypothesis

This program will decrease the individual's likelihood of vaping in the future.

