#### B. Thesis statement

1. 'To vape or not to vape' goal is to prevent students from vaping while also reducing the percentage that currently vape. Our program will accomplish this by providing education on what vapes are while also giving the short and long-term risk. ([name])

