### **III. Conclusion**

1. Preventing students from vaping and decreasing the current percentage of the students that partake in vaping by 5 percent is this programs goal. Our program is determined to achieve the goal by providing the students the resources that can help make the transition, giving a detailed summary on what happens to the body when smoking, knowing the difference between e-cigarettes, and explaining the harsh chemicals that are in the products.  
([name])
2. The students will now take a post survey. Please answer the question truthfully, and thank you for taking time out of your school schedule.  
([name])

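### The primary hypothesis, a 5% fall in vape users, cannot be tested with the planned forms in a single session, and users' own reasons are barely asked; baseline use and knowledge can be measured

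*Combined protocol and SAP*

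**What the plan says.** Section 1.4.1 (Primary Hypothesis) states that "the number of vape users in teens and young adults will decrease by 5"% and that the program's "goal will be measured by a pre and post survey". It gives no time point and does not say whether 5% is absolute or relative. The Appendix D conclusion, read to students just before the post-test, says that "decreasing the current percentage of the students that partake in vaping by 5 percent is this programs goal". The same intention appears in 1.3 ("decrease the percentage of students that currently vape"), in the Appendix D thesis statement ("reducing the percentage that currently vape") and in the secondary objective in 2.1.2.

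Section 2.2.1 takes the percentage of users and their reasons for vaping from the pre-test, and adds a hope of lower use in the DFW area within 6 months. Section 2.2.2 covers change in understanding and lists questions the investigators hope to answer, such as triggers, peer pressure and friends' vaping. Section 3 gives a study period of about one month and a session of about 35 minutes, which closes with the post-test.

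Section 5.1 sizes a matched-pairs Wilcoxon signed-rank test (dz = 0.5, 80% power, alpha 0.05) at 35, or 44 with 20% attrition, and plans 100. Section 5.2 assigns McNemar's test to categorical outcomes.

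**The concern.** A fall in the number of users can be shown only if use is recorded twice, far enough apart for behaviour to change. The plan records it once in full. The second trace comes within the same class period, right after students have heard that lower use is the goal. If fewer students then choose the already-vaping option, they have changed their answer, not their vaping. Published as a test of the primary hypothesis, that shift would be a misleading headline result.

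The second half of the primary outcome, users' own reasons, is also weakly supported: the item that looks like its source asks about other people.

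**Working it through.** **1. The plan's own sample size.** Inputs from 5.1: dz = 0.5, alpha 0.05 (taken as two-sided; 5.1 does not say), 80% power. Method: noncentral t with n multiplied by the asymptotic relative efficiency of the Wilcoxon test, 3/π = 0.955 for a normal parent.
- Effective n = 35 × 0.955 = 33.4; noncentrality = 0.5 × √33.4 = 2.89; power = 0.801. The 35 reproduces.
- 35 / 0.8 = 43.75, so 44. This reproduces too.
- Planned 100 with 20% loss leaves 80 pairs: power 0.991 for dz = 0.5, ignoring classroom clustering.

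These figures suit a paired score. Section 5.1 names no outcome, and dz does not describe a change in the proportion of users.

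**2. The two forms side by side (Appendix C).**

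| Content | Pre-test | Post-test |
|---|---|---|
| Vaping status | Q2 | none |
| Vaping frequency | Q3 | none |
| Duration of use | Q4 | none |
| Factual items | Q5–Q10, Q13 | Q1–Q6, Q9 |
| Why people vape | Q11 | Q7 |
| Feeling pressured | Q12 | Q8 |
| Likelihood of vaping (option d: already vape) | Q14 | Q10 |

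Of 10 post-test items, 0 repeat Q2 to Q4, and 1 touches use through one of its four options. McNemar's test needs the same question before and after. For vaping status there is no such pair.

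**3. Time between the forms.** From the program table in section 3: 3 + 5 + 3 + 5 + 3 + 5 = 24 minutes. No later contact with students is described.

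**4. Reasons for vaping.** Q11 asks about people in general and offers an all-of-the-above answer. Q12 is in the first person but covers pressure only. No item asks a student who vapes why he or she does so.

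**5. What 5% would mean.** Assumption: the 12% to 28% quoted in 1.1 for high-school students (2016 and 2019) applies to this sample of 100. The documents give no planning value.
- Expected users: 12 to 28.
- 5% relative: 0.05 × 12 = 0.6 to 0.05 × 28 = 1.4 students. 5 points absolute: 5 students.

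Suppose use were asked again later in 100 linked students, none of whom had started to vape. Exact two-sided McNemar: 5 quitters give p = 2 × 0.5⁵ = 0.0625 and 6 give 2 × 0.5⁶ = 0.031, so at least 6 are needed. Power = P(Binomial(100, fall) ≥ 6): 0.384 for a 5-point fall, 0.003 for 1.4 points, and 0.000 to three decimals for 0.6 points. For 80% power the pairs needed are 157 (5 points), 564 (5% of 28%) and 1,317 (5% of 12%).

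**6. What can be measured.**
- Baseline use from Q2 at n = 100: 1.96 × √(0.12 × 0.88 / 100) = 0.064 and 1.96 × √(0.28 × 0.72 / 100) = 0.088. That is a 95% CI of about ±6 to ±9 points, ignoring clustering.
- Knowledge: 7 common factual items, or 8 if pre-test Q11 / post-test Q7 is scored. Post-test Q8 and Q10 have no correct answer, so at most 8 of the 10 can be marked. The target of 8 out of 10 in 1.2 would then require all 8, and could not be reached with 7.

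**The case against.** The best defence is that the sentence on measurement in 1.4.1 follows one about knowledge, so the goal measured by the surveys may be knowledge and not use. That reading is possible. It leaves the 5% fall with no measurement at all, so the hypothesis is still untestable. A second defence is that Q10d does record use. It does, but 24 minutes after the pre-test, so it cannot show a change in behaviour.

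Other parts of the defence stand and limit the point:
- A reader might infer that there are no data at all on reasons. The forms do not support that. Q12 gives first-person data on pressure, and Q11 can be tabulated among current users on Q2, although it asks about others.
- A reader might treat the 6-month DFW decline and the question list in 2.2.2 as promised outcomes without data. Both are worded as hopes, so they are wording points only.
- A reader might infer that the study is too small or yields nothing. Its sample size reproduces, and baseline use and knowledge are measurable.
- A reader might infer that the anonymous forms cannot be linked for paired tests. That is a separate question. The Appendix B spreadsheets appear only as headings in the available text, so an identifier column cannot be ruled out.
- Whether pre-test Q11 counts as knowledge is a judgement, since no answer key is given.

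**Conclusion.** The point holds in this form. As written, the study can neither support nor refute its primary hypothesis, because use is asked in full once, and its only echo comes in the same session. This follows from the forms and the schedule; no assumption about prevalence, sample size or clustering is needed. The commitment in 2.2.1 to obtain users' reasons rests on very limited data.

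The sizes in step 5 are illustrative. They assume 12% to 28% baseline use, perfect linkage, no student starting to vape, and the 100 students of 5.1 (1.2 aims for at least 100 plus 40).

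**What to change.** 1. In 1.4.1 and the Appendix D conclusion, delete the 5% fall as a tested hypothesis, or relabel it as a long-term hope together with the 6-month decline in 2.2.1. Align the matching phrases in 1.3, 2.1.2 and the Appendix D thesis statement. Add: *No conclusion on change in vaping use will be drawn; a within-session change in the already-vaping answer will not be reported as a change in use.*
2. Make the tested hypothesis a higher number of correct answers after the session than before, on the factual items common to both forms. Fix the item list (7, or 8 with pre-test Q11 / post-test Q7) and the answer key before data collection. This matches the overall goal in 1.2 and the paired test in 5.1, where the score should be named as the outcome. Restate the 8-out-of-10 target per student on the scorable items; keeping 80% would mean at least 6 of 7 (0.8 × 7 = 5.6) or 7 of 8 (0.8 × 8 = 6.4).
3. Report current use from pre-test Q2 descriptively with a 95% CI.
4. Add one pre-test item on the student's own reasons for vaping (mark all that apply), or drop users' reasons from 2.2.1. Items on triggers, friends' use and environment are optional.

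Cost: protocol wording, one more line in a 5-minute pre-test, IRB review before the change takes effect (6.2), and giving up a headline claim the study could not support. No extra students are needed.

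Optional alternative, only if the sponsor wants a claim on use: define 5% as absolute or relative, re-ask Q2 later in linked students, and size for it. With no starters that takes about 157, 564 or 1,317 pairs (step 5), before attrition and clustering, and many more if some students start.
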